To evaluate the efficacy of CLE-400 for the treatment of chronic pruritus in subjects with NP	
Primary Efficacy Endpoint:
 
 Percent change from baseline in weekly mean of the daily 24-hour WI-NRS score at Week 4. 
Secondary Efficacy Endpoints:
 
 Proportion of subjects achieving \geq 4-point decrease from baseline in weekly mean of the daily 24-hour WI-NRS score at Week 4. PGI-C ratings at Week 4. 
Exploratory Efficacy Endpoints:
 
 Percent change from baseline in weekly mean of the daily 24-hour WI-NRS at Week 2. Change from baseline in weekly mean of the daily 24-hour WI-NRS at Week 4. Proportion of subjects achieving \geq 3-point decrease from baseline in weekly mean of the daily 24-hour WI-NRS score at Week 4. Change in PGI-S ratings from baseline to Week 4. Proportion of subjects achieving improvement (“Much improved” or “Very much improved”) according to the PGI-C at Week 4. Change from baseline in weekly mean of daily sleep quality NRS at Week 4. Change from baseline in weekly mean of daily pain NRS at Week 4. Change from baseline in ItchyQoL at Week 4.
Secondary Objectives	
To evaluate the safety and local tolerability of CLE-400 in subjects with chronic pruritus associated with NP	
Secondary Safety Endpoints:
 
 Incidence of TEAEs. Change from baseline in vital signs, clinical laboratory parameters, ECGs, and ESS. Local Tolerability Assessment (LTA).

Name of Sponsor/Company: Clexio Biosciences Ltd.	Name of Study Treatment: CLE-400 or Vehicle	Name of Active Ingredient: Detomidine HCl monohydrate		
To evaluate the plasma concentration of detomidine in subjects with chronic pruritus associated with NP	
Secondary PK Endpoints:
 
 Measurement of plasma concentrations of detomidine in subjects receiving active treatment. 			

Abbreviations: TEAE, Treatment Emergent Adverse Event; ECG, Electrocardiogram; ESS, Epworth Sleepiness Scale; ItchyQoL, Itching Quality of Life; LTA, Local Tolerability Assessment; NP, Notalgia Paresthetica; NRS, Numeric Rating Scale; PGI-C, Patient Global Impression of Itch Change; PGI-S, Patient Global Impression of Itch Severity; WI-NRS, Worst Itch Numeric Rating Scale.
				

Study Design:
				

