
 1. Adult male or female subject aged 18 to 80 years, inclusive, at the time of consent. 2. Subject has a confirmed diagnosis of NP as per the investigator (board certified dermatologist) based on localized pruritus in a circumscribed, mostly unilateral area in the scapular/mid-back region, with or without pigmentation changes. 3. Subject is suffering from chronic pruritus at the relevant skin area for ≥ 3 months (information obtained from medical chart or subject's physician, or directly from the subject) prior to the screening visit. 4. [REDACTED] 5. Subject has a caregiver who can apply the gel on the affected skin area daily in the mornings, or subject is able to self-apply the gel on the affected skin area (confirmation of ability to appropriately self-apply the gel should be done at screening). 6. Subject is willing and able to complete a daily e-diary for the duration of the study and was compliant in reporting WI-NRS via the e-diary during the 7-day run-in period (i.e., reported WI-NRS at least 4 out of the 7 days during the 7-day run-in period). 7. [REDACTED] 8. For a subject who performs strengthening and stretching exercises specific for NP, subject has been performing these exercises for a minimum period of 14 days prior to the run-in period and agrees not to change his/her routine (type and frequency) throughout the study. 9. For a subject who is having massages, and/or physical therapy, and/or is using cervical soft collars for the treatment of NP, subject must have been using any of these therapies for a minimum period of 14 days prior to the run-in period and agrees not to change his/her routine throughout the study. 		

Name of Sponsor/Company: Clexio Biosciences Ltd.	Name of Study Treatment: CLE-400 or Vehicle	Name of Active Ingredient: Detomidine HCl monohydrate

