
Name of Sponsor/Company: Clexio Biosciences Ltd.	Name of Study Treatment: CLE-400 or Vehicle	Name of Active Ingredient: Detomidine HCl monohydrate

physical/laboratory/ECG/vital signs abnormality that would, in the opinion of the investigator, put the subject at undue risk or interfere with interpretation of study results.
		

32. Subject has received a nonbiological investigational product or device within 4 weeks prior to the run-in period (Day -7) or has received any investigational biological agent within 12 weeks or 5 half-lives (whichever is longer) prior to the run-in period (Day -7).
 
33. Planned major surgery during the clinical study.
 
34. Sponsor or CRO employees or employees under the direct supervision of the investigator and/or involved directly in the trial, or their family members/subjects in same household.
 
35. In the opinion of the investigator, the subject is unsuitable for participating in the study.
		

Statistical methods:
		

The significance level of this study will be 0.05, 2-sided.
 
A fixed sequence gatekeeping (hierarchical) approach will be applied to adjust for multiplicity and to control type I error due to multiple efficacy endpoints testing of the primary and secondary endpoints. The sequence order is according to the defined order of the primary and secondary endpoints. If the primary analysis is statistically significant at the 2-sided 0.05 level, the secondary endpoints will be analyzed sequentially according to the order of the secondary endpoints as listed above. A secondary endpoint will only be considered statistically significant at the 2-sided 0.05 level if the previous secondary or primary endpoint in the hierarchy is significant at the 2-sided 0.05 level.
 
.
		

Analysis sets:
		

The Intent-To-Treat (ITT) Analysis Set will include all randomized subjects. In this analysis set, treatment is assigned based on the treatment to which subjects were randomized, regardless of which treatment they actually received.
		

The Full Analysis Set (FAS), which is a subset of the ITT Analysis Set, will include all randomized subjects who received at least 1 dose of study treatment and have both baseline and at least one postbaseline WI-NRS evaluation. In this analysis set, treatment is assigned based on the treatment to which subjects were randomized, regardless of which treatment they actually received.
		

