
The Safety Analysis Set includes all subjects who receive at least 1 dose of study treatment.
		

The ITT Analysis Set will be used for summaries of subject demographics and baseline variables.
		

Name of Sponsor/Company: Clexio Biosciences Ltd.	Name of Study Treatment: CLE-400 or Vehicle	Name of Active Ingredient: Detomidine HCl monohydrate
The FAS Analysis Set will serve as the principal analysis set for efficacy inference.		
The Safety Analysis Sets will be used for analyses of safety variables.		
Efficacy Analyses:		
Efficacy will be evaluated on the basis of the FAS analysis set.		
For all WI-NRS endpoints (% change and change from baseline and proportion of subjects), the weekly mean of the 24-hour WI-NRS will be defined as the sum of the daily 24-hour WI-NRS score reported during a specific week of the study (e.g., Days 1 to 7, Days 8 to 14, Days 15 to 21, etc.) divided by the number of days with nonmissing scores for that week. For all WI-NRS endpoints, the baseline score will be defined as the average of all nonmissing daily 24-hour WI-NRS scores over the run-in period (Day -7 to Day -1); at least 4 completed WI-NRS assessments will be required during the run-in period.		

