For the primary efficacy endpoint, the percent change from baseline in weekly mean of daily 24-hour WI-NRS, the statistical model to be used for inference will be the Mixed Models Repeated Measures (MMRM) analysis using the SAS® MIXED procedure with the REPEATED subcommand. The model will include terms for treatment, categorical Week in study (1, 2, 3, and 4), treatment by week interaction, pooled sites, Baseline weekly mean WI-NRS and Baseline weekly mean WI-NRS by week interaction. The percent change from baseline in the weekly mean of daily 24-hour WI-NRS score will be the response variable in the model. The model derived least squares means of percent changes at Week 4 will be compared between the CLE-400 group and the vehicle group. The model will use the unstructured covariance matrix, the Restricted Maximum Likelihood (REML) estimation method, and the Kenward Roger adjustment method for the degrees of freedom. In the case that the model does not converge, the Maximum-Likelihood estimation method will be used instead of the default REML. If the model still does not converge, then a simpler covariance structure with fewer parameters will be used according to the following order: heterogeneous autoregressive (1), heterogeneous compound symmetry, autoregressive (1), and compound symmetry.		
Safety Analyses:		
Safety analyses will include TEAEs, LTA, laboratory tests, vital signs, ESS scores, and ECGs.		
No inferential statistics will be done on safety variables.		
Pharmacokinetic Analyses:		
Detomidine concentration data will be listed per subject and summarized by visit, dose and nominal timepoints using descriptive statistics.		

Name of Sponsor/Company: Clexio Biosciences Ltd.	Name of Study Treatment: CLE-400 or Vehicle	Name of Active Ingredient: Detomidine HCl monohydrate
Sample Size Consideration:		

The sample size was determined based on the following assumptions: a difference of 24% in the percent change from baseline to Week 4 in WI-NRS between CLE-400 and vehicle, a randomization ratio of 1:1, a standard deviation (SD) of 30%, a power of 81%, a 2-sided alpha level of 0.05, and an overall drop-out rate of 5%.
 
Under the above assumptions, the estimated number of subjects required for this study is 54 subjects (27 subjects per treatment arm).
		

SPONSOR:

Clexio Biosciences Limited

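### Does the lack of a minimum number of diary days for post-baseline weekly WI-NRS means leave the Week 4 endpoints open to choice?

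*Combined protocol and SAP*

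**What the plan says.** Everything available on this point is in section 1.1, Synopsis.

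- **Weekly mean** (Statistical methods, Efficacy Analyses). The daily scores reported in a study week are summed and "divided by the number of days with nonmissing scores for that week". The definition is introduced as applying to every WI-NRS endpoint: percent change, change, and proportion of subjects.
- **Baseline.** A minimum of 4 completed assessments applies to the run-in. Inclusion Criterion 6 uses the same threshold for diary compliance: "reported WI-NRS at least 4 out of the 7 days during the 7-day run-in period". No minimum is given for later weeks.
- **Endpoints.** The primary is percent change in the weekly mean at Week 4. The first secondary is the proportion of subjects with at least a "4-point decrease from baseline in weekly mean of the daily 24-hour WI-NRS score at Week 4".
- **Hierarchy.** "A secondary endpoint will only be considered statistically significant at the 2-sided 0.05 level if the previous secondary or primary endpoint in the hierarchy" is itself significant. The responder endpoint therefore stands between the primary endpoint and PGI-C.
- **Primary model.** An MMRM on weekly percent change over Weeks 1 to 4, in the Full Analysis Set, which requires one post-baseline WI-NRS evaluation.
- **Sample size.** The assumptions are "a difference of 24% in the percent change from baseline to Week 4 in WI-NRS between CLE-400 and vehicle", "a standard deviation (SD) of 30" per cent, "a 2-sided alpha level of 0.05" and "an overall drop-out rate of 5" per cent, giving 54 subjects.

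**The concern.** The sponsor set a diary threshold for the run-in and none for Week 4, where the main endpoints are read. A subject who reports once in Week 4 contributes a mean based on one evening, with the same weight as a mean of seven. Criterion 6 admits subjects who miss up to three of seven run-in diaries, so sparse weeks can be expected.

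Two things could be at stake. The first is precision of the primary endpoint. The second is the responder endpoint: a short week is more easily misread against a fixed 4-point cut, and with about 26 subjects per arm one subject can move a borderline p-value. If the handling of a sparse week were open, it could be settled after the data are seen, on an endpoint that gates PGI-C.

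**Working it through.** **1. The plan's own sample size.** Inputs from Sample Size Consideration: difference 24, SD 30, two-sided alpha 0.05, power 81%, drop-out 5%.

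- n per arm = 2 × [30 × (1.960 + 0.878)/24]² = 25.2, rounded up to 26.
- 52/0.95 = 54.7, against 54 stated.
- t-test power at 26 per arm is 80.7%.

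The stated figure is reproduced to within a subject or so, and it does not depend on any diary rule.

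**2. How many sparse Week 4s?** These inputs are assumptions; the documents give no diary completion rate.

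- Diary gaps: with daily completion p, the expected number with 1 to 3 scores is 52 × P(1 ≤ Bin(7, p) ≤ 3). This gives 0.1, 1.7 and 6.5 subjects at p = 90%, 80% and 70%.
- Drop-out: 54 × 0.05 = 2.7 subjects. If stopping is uniform over 28 days and the diary stops with treatment, 2.7 × 3/28 = 0.3 have 1 to 3 Week 4 scores and 2.7 × 21/28 = 2.0 have none.

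**3. Cost to the primary endpoint.** Assume a within-subject daily SD of s = 1.0, 1.5 or 2.0 points, independent days and a mean baseline of 7.2. On the percent scale the day-to-day error of a k-day mean is e(k) = 100s/(7.2√k). With m of 52 subjects having k days, variance = 30² + (m/52)(e(k)² − e(7)²).

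| Case | s | e(k) | e(7) | Variance | Power |
|---|---|---|---|---|---|
| all full weeks | – | – | – | 900 | 80.7% |
| k = 1, m = 2 | 1.0 | 13.9 | 5.2 | 906 | 80.5% |
| k = 1, m = 3 | 2.0 | 27.8 | 10.5 | 938 | 79.1% |
| k = 3, m = 3 | 1.0 | 8.0 | 5.2 | 902 | 80.7% |
| k = 3, m = 3 | 2.0 | 16.0 | 10.5 | 908 | 80.4% |

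**4. Would a minimum do better?** Compare the variance of an arm's Week 4 mean with the short week kept against the variance with it set to missing and recovered through Weeks 1 to 3. With 1 to 3 sparse subjects of 26 and an assumed compound-symmetric correlation of 0.5, 0.7 or 0.9, the ratio of keeping to dropping is 0.94–1.07 for one day, 0.93–1.02 for two and 0.93–1.00 for three. Neither rule is clearly better.

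**5. Responder status of a sparse week.** The definition covers proportions of subjects and divides by the days present. One to three scores therefore give a mean, a change from baseline and a responder status. Excluding such a subject or recoding to non-response would depart from the text.

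**6. Misclassification.** For a true 3.0-point fall, the chance of being read as a response is P(N(3.0, s²/k + s²/7) ≥ 4):

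| Days in Week 4 | s = 1.0 | s = 1.5 | s = 2.0 |
|---|---|---|---|
| 1 | 17.5% | 26.6% | 32.0% |
| 3 | 7.4% | 16.7% | 23.4% |
| 7 | 3.1% | 10.6% | 17.5% |

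By symmetry, a true 5.0-point fall is missed equally often. At the larger daily SDs, more than half of the three-day error is already present with seven full days.

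**7. The empty Week 4.** Here the definition gives no value. Take one such subject per arm, about the number in step 2, and 13 v 6 responders. Counting the two as non-responders gives 13/27 v 6/27, p = 0.046; excluding them gives 13/26 v 6/26, p = 0.044 (uncorrected chi-square, assumed because section 1.1 names no test).

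**The case for a change.** The strongest reply is that the responder endpoint carries alpha and has few subjects. Taking 13/26 v 6/26, p is 0.044 as observed, 0.063 if one sparse responder in the active arm is excluded (12/25), and 0.080 if that subject is counted as a non-responder (12/26). At assumed rates from 40% v 15% to 60% v 30%, recoding one observed responder in the active arm to non-response turns p < 0.05 into p ≥ 0.05 in 10% to 11% of trials.

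The arithmetic is right, but it describes alternatives that the definition does not permit: a sparse responder is a responder. It is also conditional. For an active-arm subject chosen without regard to response, the figure falls to 4.5% to 6.2%. At 90% diary completion, the chance that the active arm has any sparse Week 4 from diary gaps is about 7%. The worked example depends on the test too: Fisher's exact test gives p = 0.083 for both 13/26 v 6/26 and 12/25 v 6/26.

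Two parts stand. Section 1.1 does not say how a subject with no Week 4 scores counts as a responder, and it lists no sensitivity analysis by diary days. The choice for an empty week could matter more than in step 7 if such subjects fell in one arm. But section 1.1 gives no test or missing-data rule for either secondary endpoint, so it is evidently not where that detail is placed. The fuller statistical text was not available, and silence in a synopsis does not show that the plan is silent.

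**Conclusion.** No change follows. The all-available-days rule is explicit, applies equally to both arms and covers the responder endpoint. No directional bias has been shown. Its cost to the primary endpoint is at most about 1.6 percentage points of power (80.7% to 79.1%) in the cases examined, and a minimum-days rule would bring no clear gain. These figures rest on assumed values: daily SD 1 to 2 points, mean baseline 7.2, independent days and no more than three one-day Week 4 values. A much larger share of one-day weeks would cost more.

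What remains is a gap in detail: the responder status of about two subjects with an empty Week 4, and an optional sensitivity table. Analysts settle such points routinely before unblinding, and the full statistical section may already do so. Following the plan as written gives no wrong result.

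### Low priority: if the primary REML model does not converge, the ML fallback on the same unstructured matrix makes the Week 4 SE about 3% to 7% too small; retry REML first

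*Combined protocol and SAP*

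**What the plan says.** All the text is in 1.1 Synopsis.

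- **Planned model.** Efficacy Analyses specifies "the unstructured covariance matrix, the Restricted Maximum Likelihood (REML) estimation method, and the Kenward Roger adjustment method". The mean model includes treatment, "categorical Week in study (1, 2, 3, and 4), treatment by week interaction, pooled sites", baseline, and baseline by week. Site is a main effect with no site-by-week term.
- **First fallback.** "In the case that the model does not converge, the Maximum-Likelihood estimation method will be used instead of the default REML". Nothing else changes at this step.
- **Second fallback.** "If the model still does not converge, then a simpler covariance structure with fewer parameters will be used according to the following order". Four structures are then named, in this sequence: ARH(1), CSH, AR(1), CS.
- **Level.** Statistical methods states "The significance level of this study will be 0.05, 2-sided" and sets up a fixed sequence: "If the primary analysis is statistically significant at the 2-sided 0.05 level, the secondary endpoints will be analyzed sequentially".

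The synopsis does not say whether Kenward-Roger is kept under ML, or whether the simpler structures are fitted by ML or REML. It gives neither the number of pooled sites nor any between-week correlations.

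**The concern.** The first fallback keeps the hardest part of the model, the 10 covariance parameters, and changes only the estimator. REML allows for the degrees of freedom spent on the fitted means and ML does not. In a trial of about 50 subjects, that lowers the estimated Week 4 variance enough to matter for a test at exactly 5%.

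If the fallback is used, the primary test is liberal and its confidence interval is too narrow. Because the primary result opens the gate to both secondary endpoints, the excess error passes down the sequence. A reader of the results could fairly ask why a convergence problem led to a more lenient test.

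**Working it through.** **Inputs from the synopsis (Sample Size Consideration).** Difference 24 percentage points, SD 30, two-sided alpha 0.05, power 81%, drop-out 5%, 27 per arm.

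**The plan's own figure.** Per arm, n = 2 × (1.960 + 0.878)² × (30/24)² = 25.2. Dividing by 0.95 gives 26.5, so 27 per arm and 54 in total. This reproduces the plan.

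**Covariance parameters.** Unstructured over 4 weeks: 4 × 5 / 2 = 10. ARH(1) and CSH have 5 each; AR(1) and CS have 2 each.

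**Closed form.** Subjects at Week 4: n = 54 × 0.95 ≈ 51. Mean parameters per week: p = 3 + (pooled sites − 1). The ratio of ML SE to REML SE is sqrt((n − p)/n). Size is the two-sided tail of t on n − p df beyond ratio × t(0.975). The 95% half-width is t × 30 × sqrt(1/26 + 1/25) × ratio. Under REML it is 2.011 × 8.40 = 16.9 points.

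| Pooled sites (assumed) | p | SE ratio | Size | ML half-width |
|---|---|---|---|---|
| 1 | 3 | 0.970 | 5.7% | 16.4 |
| 3 | 5 | 0.950 | 6.2% | 16.1 |
| 4 | 6 | 0.939 | 6.5% | 15.9 |
| 6 | 8 | 0.918 | 7.1% | 15.6 |

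The closed form charges every site parameter fully to Week 4. The planned model has a site main effect only, so with more than one site these rows overstate the problem. Simulation is the better guide.

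**Simulation of the model as written.** Null data, Week 4 SD 30. A and B have 27 per arm, about 5% drop-out, correlation 0.7 and Kenward-Roger on both fits; C takes 51 subjects. Entries are for 1 / 3 / 6 pooled sites.

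| Simulation | ML SE shortfall | ML size | REML size |
|---|---|---|---|
| A: 4,500 trials per setting | 2.9 / 4.3 / 6.5% | 5.6 / 5.5 / 6.6% | 4.8 / 4.6 / 5.0% |
| B: 1,200 per setting, size from SE and df against the true SE | 2.9 / 3.8 / 5.4% | 5.7 / 5.9 / 6.2% | 5.0 / 4.9 / 4.8% |
| C: n = 51 | 3.0 / 4.5 / 6.8% | 5.6 / 6.4 / 6.3% | 5.1 / 5.4 / 4.7% |

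Monte Carlo SE in A is 0.3 to 0.4 points. Within the same trials, ML exceeds REML by 0.7–0.8, 0.9–1.0 and 1.6–1.7 points for 1, 3 and 6 sites. Over nine assumed correlation, SD and site settings in A, ML runs at 5.5% to 7.1% (mean 6.1%) and REML at 4.5% to 5.4% (mean 5.0%). The three six-site settings give ML 6.1%, 6.6% and 7.1%.

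**Kenward-Roger.** In B, adding its SE adjustment to the ML fit moves the size by 0.1 point or less. The ML degrees of freedom come out higher than under REML (53.5 to 55.7, against 48.8 to 50.5), which does not help.

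**Interval width.** Mean SE times t from B, for 1 / 3 / 6 sites:
- REML: 8.350 × 2.008 = 16.8; 8.451 × 2.009 = 17.0; 8.643 × 2.010 = 17.4.
- ML: 8.108 × 2.005 = 16.3; 8.129 × 2.005 = 16.3; 8.181 × 2.003 = 16.4.

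**Overall alpha.** 0.05 + q × (size under ML − 0.05), with q the assumed probability that ML is needed and convergence taken as unrelated to the test result. For ML size 5.5% to 7.1%:
- q = 1%: 0.05005 to 0.05021.
- q = 5%: 0.05025 to 0.05105.

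REML failed in none of 40,500 fits in A and none of 9,200 data sets in B. Both used purpose-written code on clean normal data, not SAS on real diaries.

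**The case against.** **The branch may never be used.** This stands. With four weeks, about 51 subjects and one treatment contrast, the REML fit should nearly always converge. The sizes above are also averages over all simulated trials; the size among trials where REML actually fails is unknown. A reader might infer that the trial's type I error is materially inflated. The documents do not support that: the planned analysis holds 5%, and overall alpha moves in the fourth decimal place or, at most, by about 0.001.

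**The six-site figure is soft.** This also stands. One could quote about 7%, but that is the closed-form bound, or the least favourable of the simulated correlation patterns, in which REML itself ran at 5.4%. The plan has no site-by-week term and the number of pooled sites is not given. About 6% to 7% is as much as can be said.

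**ML is not the worst fallback on the list.** This stands in part. ML keeps the matrix unstructured. With model-based SEs, the plan's next step, ARH(1), ran from 2.8% to 8.0% in A, and the other structures from 3.1% to 8.3%, because a wrong structure can err in either direction. A reader might therefore infer that deleting the ML sentence is enough, or that the structured steps are safer. Neither follows. The gain comes from retrying the same matrix by REML before anything else changes.

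**Convergence steps may be set out elsewhere.** The text examined is the synopsis. If fuller statistical text already calls for REML restarts before ML, the point is met.

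**Conclusion.** The point holds at low priority, as an optional improvement. When the fallback is used, the Week 4 SE is about 3% to 7% too small, and the nominal 5% test runs at about 5.5% to 6.5%, or about 6% to 7% with six pooled sites. Kenward-Roger does not correct this.

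The direction is not in doubt: it follows from how ML estimates variance, and the closed form and three simulations agree. The size rests on assumptions the documents do not settle: the number of pooled sites, the between-week correlations, the SDs at Weeks 1 to 3, drop-out at random, and Kenward-Roger being kept under ML.

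This is not a fault in the planned primary analysis or a threat to the trial's overall error rate. It is a fallback that departs from the stated level when a simple first step could avoid it.

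**What to change.** Replace the sentence that switches to ML with, for example:

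> *Should the unstructured REML fit fail to converge, it will be repeated with alternative starting values or an equivalent parameterisation of the same matrix (for example Cholesky), keeping Kenward-Roger. If it still fails, the simpler structures will be fitted by REML in the order listed.*

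The second sentence also settles which estimator applies at the later steps.

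**Optional, for the sponsor's statistician to decide:** at the structured steps, base the Week 4 test on a small-sample (leverage-corrected) sandwich SE. In simulation A this gave 4.4% to 6.2% across the four structures, whereas the uncorrected sandwich gave 5.5% to 7.7%, no better than ML. The corrected result was not reproduced in the other simulations, its degrees of freedom would have to be set by hand, and it has not been shown to run in the SAS procedure the plan names. It is a judgement call and not part of the core change.

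**Cost.** Two sentences before unblinding and little or no programming unless the optional step is taken. No new data and no more subjects. If the REML retry succeeds, the interval is slightly wider than ML would give (about 16.9 against 16.2 to 16.4 percentage points), the same as the planned analysis. Simulated power at a 24-point difference for 1 / 3 / 6 sites is that of the planned analysis, 80% / 80% / 77%, against a nominal 82% / 82% / 81% under ML. ML gains that difference only by exceeding 5%.

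### The last two covariance fallbacks assume one variance for Weeks 1 to 4, so in the unlikely event that they are reached, the Week 4 test's 5% level is not protected

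*Combined protocol and SAP*

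**What the plan says.** Section 1.1 (Synopsis, Efficacy Analyses) models percent change from baseline in weekly mean WI-NRS over Weeks 1 to 4. The fixed effects are treatment, week, treatment by week, pooled sites, baseline, and baseline by week. The inference is at the last week: "The model derived least squares means of percent changes at Week 4 will be compared between the CLE-400 group and the vehicle group".

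The covariance is unstructured, with REML and Kenward-Roger degrees of freedom. If the fit does not converge, ML replaces REML. If it still does not converge, simpler structures follow in this order: "heterogeneous autoregressive (1), heterogeneous compound symmetry, autoregressive (1), and compound symmetry". The synopsis names no robust standard error for any of these steps.

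Under Statistical methods, "The significance level of this study will be 0.05, 2-sided", and the primary result gates the two secondary efficacy endpoints in a fixed sequence. The only SD given is in the sample size paragraph and refers to the change at Week 4.

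**The concern.** The four fallback structures fall into two kinds. Heterogeneous AR(1) and heterogeneous compound symmetry estimate a separate variance for each week, so the Week 4 standard error uses a Week 4 variance. Homogeneous AR(1) and homogeneous compound symmetry estimate one variance for all weeks. Treatment and baseline both interact with week, so with complete data the Week 4 difference itself hardly depends on the structure. What changes is its standard error.

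If the early weeks are less variable than Week 4, the pooled variance is too small for the Week 4 contrast and the test rejects too often. Kenward-Roger does not repair this: it allows for having estimated the chosen covariance, not for having chosen a wrong one. At stake is the level of the primary test, and through the gate the level of the two secondary tests.

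**Working it through.** **Inputs from Section 1.1, Synopsis.** Two-sided alpha 0.05; "a difference of 24% in the percent change from baseline to Week 4 in WI-NRS between CLE-400 and vehicle"; "a standard deviation (SD) of 30" (percent); "a randomization ratio of 1:1"; power 81%; "an overall drop-out rate of 5" (percent); 54 subjects, 27 per arm.

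**Step 1. The plan's own figure.** n per arm = 2 × (1.960 + 0.878)² × (30/24)² = 25.2, rounded up to 26, or 52 in total. Dividing by 0.95 gives 54.7, or 55, against the plan's 54. A two-sample t-test with 26 per arm has 80.7% power (82.2% by the normal approximation). The plan's figure is reproduced to within rounding, so 30% can be taken as the Week 4 SD and 26 per arm as the evaluable number.

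**Step 2. Formula.** Under a homogeneous structure the variance behind the Week 4 test is close to the mean of the four weekly variances. Then

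- SE used / true SE = √(mean weekly variance / Week 4 variance)
- type I error ≈ 2 × [1 − Φ(1.96 × that ratio)]

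Example, SDs 20/25/28/30: the mean variance is (400 + 625 + 784 + 900)/4 = 677.25. The ratio is √(677.25/900) = 0.867, and 1.96 × 0.867 = 1.70, so the error is 8.9%. With 26 per arm the true SE is 30 × √(2/26) = 8.32 points, and the SE used is 26.02 × √(2/26) = 7.22.

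**Step 3. Results.** The Week 1 to 3 SDs are assumptions; only the Week 4 value comes from the plan.

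| SDs, Weeks 1–4 | Mean variance | SE ratio | Formula | Simulation A | Simulation B |
|---|---|---|---|---|---|
| 34/32/31/30 | 1010.25 | 1.059 | 3.8% | not run | 4.0–4.5% |
| 30/30/30/30 | 900 | 1.000 | 5.0% | 4.8–5.7% | 4.8–5.8% |
| 24/27/29/30 | 761.5 | 0.920 | 7.1% | 6.8–8.1% | 6.7–7.8% |
| 20/25/28/30 | 677.25 | 0.867 | 8.9% | 8.4–9.0% | 8.5–9.3% |
| 16/22/27/30 | 592.25 | 0.811 | 11.2% | 10.8–12.5% | not run |
| 15/22/27/30 | 584.5 | 0.806 | 11.4% | not run | 10.9–12.0% |

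- Simulation A: 3,000 null trials per setting, 26 per arm, complete data, AR(1) and compound symmetry fitted by REML, tested on 50 df.
- Simulation B: 4,000 null trials per setting, 54 subjects, 5% drop-out, the plan's fixed effects with four pooled sites assumed, and 46 or 150 df standing in for Kenward-Roger.
- Both assume true correlations of AR(1) 0.85 or compound symmetry 0.7. The 34/32/31/30 row was simulated under AR(1) 0.85 only.
- Monte Carlo standard error at 5% is √(0.05 × 0.95/3000) = 0.4 points for A and 0.3 points for B.

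**Step 4. Comparator.** When the Week 4 variance is estimated separately, the error stays near nominal for every pattern: 4.7% to 5.7% with an unstructured covariance (A) and 5.2% to 5.3% with a Week 4 ANCOVA (B).

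**Step 5. How likely these steps are to be reached.** The unstructured matrix has 4 variances and 6 covariances, 10 parameters for 54 subjects. In 496 simulated null trials, covering three SD patterns and three correlation settings with normal data and 5% drop-out, the unstructured REML fit never failed. The optimiser was purpose-written, not SAS. The approximate 95% upper bound on failure at the first step is 3/496 = 0.6%. Even if every such failure went on to a homogeneous structure with 12% error, the overall error would rise by at most about 0.006 × (12 − 5) = 0.04 points.

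**The case against.** The strongest reply is that the plan already orders the structures sensibly. Both heterogeneous forms come before either homogeneous one, and four fits (unstructured REML, unstructured ML, heterogeneous AR(1), heterogeneous compound symmetry) must fail before the issue arises. That stands, and it is why the priority is low.

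A reader might infer that the Week 4 test, once on these steps, does exceed 5%. The documents do not support that. They give no SD for Weeks 1 to 3 and do not say that variance grows. Growth is plausible for a change score, because Week 1 follows directly on the run-in, but it is an assumption. With constant variance the level holds, and with larger early variance the test is conservative.

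A reader might also take the 7% to 12% as error rates in trials where the earlier fits have failed. They are not: the simulations fitted the homogeneous structures to ordinary datasets, and the error rate among non-convergent ones is unknown.

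Finally, the text reviewed is the synopsis. A robust standard error could be specified in a fuller statistical section, and its absence from the synopsis does not show that none is planned.

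What remains is that a last-resort rule for the primary test has a level that depends on an equal-variance assumption, which the synopsis neither states nor supports.

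**Conclusion.** The point holds in conditional form. If homogeneous AR(1) or compound symmetry is reached, the 5% level of the Week 4 test is not protected. It is about 6% to 9% for SDs rising moderately to 30%, about 11% to 12% for a steep rise, about 5% for constant SDs, and about 4% for falling SDs. These figures rest on the plan's Week 4 SD, assumed SDs for the earlier weeks, assumed correlations, normal data, and datasets not selected for non-convergence. Because the steps are very unlikely to be reached, the effect on the trial's overall type I error is very small. This is an inexpensive improvement to the plan and does not threaten the primary analysis as specified.

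**What to change.** Replace the two homogeneous structures so that every fallback keeps week-specific variances. Use heterogeneous Toeplitz (4 variances and 3 correlations, 7 parameters), then heterogeneous AR(1), then heterogeneous compound symmetry (5 parameters each).

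If none converges, make the primary comparison an ANCOVA of the Week 4 percent change on treatment, pooled sites and baseline weekly mean WI-NRS. It needs no iterative covariance fit and uses only the Week 4 variance.

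If the sponsor prefers to keep a homogeneous structure as the last step, state that it will be used with a small-sample-corrected sandwich standard error.

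The change is one sentence in the protocol and SAP. The ANCOVA has a cost: it drops subjects with no Week 4 mean, about 0.05 × 54 = 2.7, or roughly 3 of 54. It therefore gives up the information from their earlier weeks, but only if every heterogeneous structure has failed. The sandwich option avoids that loss. Which of the two to use is a matter of preference, but it should be fixed before unblinding.
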